**Table 2. Message sets for formative message testing in a 2x3 between subjects experiment (Aim 1 Phase 2)**

		THREAT	
		ABSOLUTE RISK (AR)	RELATIVE RISK (RR)
EFFICACY	Quit only (Q)	Set 1: AR/Q (n = 8)	Set 2: RR/Q (n = 8)
	Switch only (S)	Set 3: AR/S (n = 8)	Set 4: RR/S (n = 8)
	Combined quit + switch (QS)	Set 4: AR/QS (n = 8)	Set 6: RR/QS (n = 8)

**Aim 1, Phase 1: Study 2 –ONLINE RATING SURVEY:** In Phase 1, Study 2 we will conduct an online survey to quantitatively examine young adults’ perceptions of 8 absolute risk and 8 relative risk anti-tobacco messages and quit/switch efficacy statements. To reduce participant burden, each participant will view a random sample of messages as follows: n = 5 absolute and relative risk anti-tobacco messages (of N = 24), and n = 3 (of N = 12) efficacy messages. They will be asked to rate absolute and relative risk antitobacco messages and quit/switch efficacy statements for perceived message effectiveness, likeability, and reactance.

**Aim 1, Phase 1: Study 3 –IN-DEPTH INTERVIEWS:** Interviewees will be asked to share their reactions to the 24 textual anti-tobacco messages tested in Study 2. Specifically, interviewees will be asked to rate their top 5 (of N =12) absolute risk and top 5 (of N =12) relative risk antitobacco messages. We will then qualitatively explore their rationale for their top 5 selected messages.

**Aim 1, Phase 2: ONLINE FACTORIAL EXPERIMENT** (NCT05393869): Using a 2x3 factorial experiment (Table 2), plus control group design we will test the influence of AR and RR message framing on perceived effectiveness, tobacco risk perceptions, and behavioral intentions in young adult ever polytobacco users. Participants will be randomized to one of 8 conditions, including 6 experimental sets of AR and RR anti-tobacco messages (Table 3) and a control set of AR or RR regulatory control messages. We will present 8 messages within each experimental and control set. An expert panel of scientists, selected and invited by the mentoring team, will review all messages, which we will further refine based on expert feedback prior to testing in Aim 1, Phase 2 (NCT05393869).

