#### **B. Aim 1, Phase 1: Study 2—ONLINE RATING SURVEY Procedures**

**Prescreening and consent.** Participants will be recruited via Prolific, an online platform open to participants who are compensated for completing surveys and online behavioral experiments. Prolific is an efficient online recruitment platform, ideal for pilot studies, as it can deliver a high number of participants, per day, at low cost (recommended, minimum \$0.175 per minute of survey participation time). Data quality provided by Prolific

samples is high and comparable to that from traditional college student samples. Prolific offers access to over 38,000 United States nationals. Prolific samples are young; approximately 1/3 of the Prolific population reports ages < 35 years old, which makes Prolific an ideal pool for recruiting young adult survey participants. Prolific is also a viable method for recruiting hard-to-reach populations for survey research, including LGBT populations.

Prescreening will be conducted via Prolific. Prolific is able to segment our population of interest for age (18-35 years) and currently residing the United States. It can also help us track gender and sexual orientation in order to balance recruitment. We are able to add in a custom pre-screening question to assess for prior history of ever nicotine or tobacco use (i.e., use of combustible tobacco or e-cigarette products at least once).

Participants who meet eligibility criteria will be directed to an online survey administered via Qualtrics. Consent will be completed online prior to the Qualtrics survey.

Qualtrics survey procedures. Following online consent, participants will be directed to complete a survey that includes questions assessing tobacco use, including exposure to tobacco related advertising, coupons, and discounts; harms perceptions and tobacco-related behavioral intentions (i.e., quit, switch). It is estimated that the survey will take 20 minutes to complete.

Participants will answer baseline survey questions before viewing a random sample of 5 messages (of N = 24); they will rate each message for perceived effectiveness, likeability, and reactance. After viewing all messages, participants will complete a post-survey and receive \$0.175/minute (estimated \$3.50) via Prolific for participating.

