### **B. Aim 1, Phase 1: Study 2-ONLINE RATING SURVEY Data Analysis**

For online rating survey data, we will describe mean and median values of participants' ratings of perceived message effectiveness, likeability, and reactance.

In exploratory analyses, we will assess whether there are systematic differences in participants' ratings by message type (AR vs RR), gender, LGBT status (vs non-LGBT), race/ethnicity, age (e.g., 18-24 vs 25-35) and tobacco user type (e.g., current, former, never polytobacco user). We will test mean differences between groups using t-tests or ANOVA. If there are violations of assumptions (e.g., normality) we will test median differences between groups using Wilcoxon rank-sum test (two groups) or Kruskal Wallis test (more than 2 groups).

We will also run exploratory regression models to evaluate the effect of risk message type (e.g., absolute risk vs. relative risk) and efficacy message type (e.g., quit; switch; combination) on messages on perceived message effectiveness, likeability, and reactance; controlling for pro- and anti-tobacco marketing exposure, baseline risk and efficacy perceptions and behavioral intentions. For models testing the effect of efficacy

messages, we will conduct overall F-tests to determine if there is an effect of efficacy message type in each model. If so, pairwise t-tests will be conducted, and Holm's procedure will be used to control Type I error rate.

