#### **D. Aim 1, Phase 2: ONLINE FACTORIAL EXPERIMENT (NCT05393869) Data Analysis**

We will fit linear regression models to evaluate the effect of condition on perceived effectiveness, risk perceptions, and behavioral intentions. Covariates will include exposure to pro- and anti-tobacco marketing, and baseline risk perception and behavioral intention items (per respective models). Baseline and post-viewing scores may be transformed if violations of assumptions are detected. We will conduct overall F-tests to determine if there is an effect of condition in each model. If so, pairwise t-tests will be conducted, and Holm's procedure will be used to control Type I error rate. Exploratory analyses will be conducted to determine if there is an interactive effect between Condition x Topic. *Responses will be examined by gender and sexual orientation to determine if there are systematic differences.*

Sample Size Justification: For the Aim 1, Phase 2: ONLINE FACTORIAL EXPERIMENT

(NCT05393869) an analytic sample size of 400 participants per group will allow us to detect the best message in terms of risk perception score with 75% probability assuming the mean score in the best group is at least 0.1 standard deviations better than the mean score in the second best group. As effect sizes of 2 or greater are reported in the literature for this outcome, we do not consider smaller differences to be of interest. As our analytic sample size is N = 2800 participants (n = 400 participants per experimental or control group); we have inflated our overall sample size is inflated by 5% to account for estimated inconsistencies between prescreening and survey responses, resulting in an overall sample size of N = 2940.

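### Study 2's exploratory tests assume independent observations although each participant rates several messages, and no single unit of analysis makes them valid for every listed factor

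*Combined protocol and SAP*

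**What the plan says.** Section III.B (Study 2 paragraph below Table 2) gives each participant "n = 5 absolute and relative risk anti-tobacco messages (of N = 24), and n = 3 (of N = 12) efficacy messages". The Study 2 procedures in IV.B confirm that the risk messages are rated one at a time: participants see a "random sample of 5 messages (of N = 24); they will rate each message for perceived effectiveness", and also rate likeability and reactance.

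Section VI.B first describes means and medians. It then looks, as exploratory work, for "systematic differences in participants' ratings by message type (AR vs RR), gender, LGBT status (vs non-LGBT), race/ethnicity, age" and tobacco user type. The tool is: "We will test mean differences between groups using t-tests or ANOVA". If assumptions fail, the fallback is the "Wilcoxon rank-sum test (two groups) or Kruskal Wallis test (more than 2 groups"). Exploratory regressions on risk-message type and efficacy-message type follow, with an F-test and Holm-adjusted pairwise t-tests for efficacy type. For Study 2 the plan names no unit of analysis, participant-level averaging, paired test, random effect or clustered standard error.

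The sample-size paragraph in VI.B describes a different layout: 500 analysed participants, 250 in each of two groups, AR and RR.

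For the Phase 2 factorial experiment, VI.D adds: "Exploratory analyses will be conducted to determine if there is an interactive effect between Condition x Topic". There each participant rates 8 messages for perceived effectiveness and reactance (IV.D).

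**The concern.** Ratings from one person tend to be alike. A test that counts five ratings as five independent observations overstates the information about anything that varies between people, such as gender, LGBT status, race/ethnicity, age or user type. The same list of tests also covers message type, which under III.B varies within a person. The two kinds of factor need different handling, and the plan offers one set of tools for both.

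What is at stake is the credibility of reported differences. LGBT status is the programme's central subgroup, and a spurious difference in how LGBT participants react would mislead. The Holm step cannot help, since it adjusts p-values that must already be valid.

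**Working it through.** **The plan's own sizing.** VI.B takes SD 1.0, difference 0.25, two-sided 0.05 and 80% power, and states 199 per group. The usual formula gives 2 × ((1.960 + 0.842)/0.25)² = 251.2, so 252 per group; 199 per group has about 70% power. The planned 250 per group has 79.8%. The 199 is a separate matter. What counts here is that the calculation uses one observation per participant and separate AR and RR groups.

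**Does any one unit fit all listed factors?**

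| Unit | Person-level subgroups | AR vs RR under III.B |
|---|---|---|
| Single rating | Invalid (clustered) | Ignores pairing |
| One mean per person | Valid | Cannot be formed for most people |
| One AR and one RR mean per person | Two values per person, still clustered | Paired, but no paired test is planned |

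The 24 messages split 12 AR and 12 RR according to the Study 3 text, which reuses them. The chance that all 5 are of one type is 2 × C(12,5)/C(24,5) = 3.7%, so about 96% see both. The Study 2 paragraph also speaks of 8 and 8; that would give 2 × C(8,5)/C(16,5) = 2.6%, and the conclusion is the same.

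**Subgroup tests with ratings as the unit.** The documents give no within-person correlation ρ, so a range is assumed. With m ratings per person the design effect is DE = 1 + (m − 1)ρ, and the true type I error is 2Φ(−1.96/√DE).

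| ρ | DE, m = 5 | Type I error | DE, m = 3 | Type I error |
|---|---|---|---|---|
| 0.1 | 1.4 | 10% | 1.2 | 7% |
| 0.2 | 1.8 | 14% | 1.4 | 10% |
| 0.3 | 2.2 | 19% | 1.6 | 12% |
| 0.5 | 3.0 | 26% | 2.0 | 17% |
| 0.7 | 3.8 | 31% | 2.4 | 21% |

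Simulation with 500 participants and 5 ratings each agrees. The same tests on participant means gave 4.9-5.9%, nominal within simulation error.

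**AR vs RR under mixed exposure (III.B).** With 1,250 ratings of each type and SD 1, the independent-sample standard error is √(2/1250) = 0.040. If messages do not differ within type, a model with a participant intercept has information (1.25 − 1.033c)/(1 − ρ) per person, where c = ρ/(1 + 4ρ) and 1.033 is the variance of the number of AR messages among 5. For 500 people the standard errors are 0.0355, 0.0305 and 0.0274 at ρ = 0.3, 0.5 and 0.6. The naive value is then 13%, 31% and 46% too wide. The naive test is slightly conservative (type I error 3.6-4.6% over ρ = 0.2-0.7) and still has over 99.9% power for 0.25 units.

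Now let messages differ within type, with variance s² as a share of the total, and let inference go beyond these messages. With 12 messages per type, the squared standard error gains 2s²/12 = s²/6. The mixed-model value passes 0.040 when s² exceeds 6 × (0.0016 − 0.0355²) = 0.2% at ρ = 0.3, 0.4% at 0.5 and 0.5% at 0.6. Beyond that the naive value is too narrow. (Against the naive estimator's own sampling error, 0.0389 at ρ = 0.3, the crossover is lower still: 6 × (0.0016 − 0.0389²) = 0.05%.) At an assumed 2% and ρ = 0.5, the naive test rejected a true null about 26% of the time in simulation.

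**AR vs RR as separate groups (sample-size text).** Message type is then a between-person factor with 5 ratings each. Rating-level tests reject 19%, 26% and 31% of the time at ρ = 0.3, 0.5 and 0.7, as in the m = 5 column.

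**The case against.** The strongest reply is that VI.B never says single ratings are the unit. Its sample-size paragraph counts participants, which points to one value per person, and on that basis the subgroup tests hold their level. The regressions are described too briefly to rule out a mixed model. This stands, so the 14-31% is conditional on an unstated choice. It does not rescue the plan, because one value per person leaves no independent-sample AR-vs-RR test under the exposure described in III.B.

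A second reply is that the tests are labelled exploratory: "In exploratory analyses, we will assess whether there are systematic differences in participants' ratings". No decision rule hangs on them, and VI.B's main analysis is descriptive. That also stands and limits the weight of the point.

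Three stronger readings are tempting, and the documents do not support them.

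- That the AR-vs-RR comparison is merely imprecise. This holds only with no message-to-message variance, where power for 0.25 units is over 99.9% anyway. With a little such variance the error runs the other way.
- That Study 2 decides which text enters Phase 2. The plan states no such rule; it cites focus-group feedback and expert review.
- That Phase 2 as a whole is affected. Risk perceptions and intentions are asked after all messages, not per message. Only outcomes rated per message are touched, and only if topic varies within a set.

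**Conclusion.** The point holds in a limited form. Study 2 collects several ratings per person, the named tests assume independent observations, and no single unit makes them right for both message type and person-level factors.

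- **Subgroups:** if ratings are the unit, type I error is about 14-31% with 5 ratings (correlation 0.2-0.7) and 7-21% with 3 efficacy ratings (0.1-0.7). If participant means are the unit, it is nominal.
- **AR vs RR, mixed exposure:** the standard error is wrong. It is too wide if messages do not differ within type. Judged against the mixed model, it is too narrow once message variance passes roughly 0.2-0.5% of the total (correlations 0.3-0.6) and inference is meant to reach beyond the tested messages.
- **AR vs RR, separate groups:** rating-level tests would reject 19-31% of the time (correlations 0.3-0.7).

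The correlations, the message variance and the 12/12 split used for exposure are assumptions. The two descriptions of exposure conflict and must be reconciled. Because the work is exploratory, the consequence is confined to how subgroup and message-type differences are reported.

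**What to change.** 1. Reconcile III.B with the sample-size paragraph of VI.B: state whether a participant sees a mix of AR and RR messages or only one type.
2. In VI.B, replace the independent-sample tests with linear mixed models. Fit one to the risk-message ratings, with message type and the subgroup factors, and a separate one to the efficacy-message ratings, with efficacy type; the two message sets are drawn separately and should not share a model. Include a participant random intercept in each. Add a message random intercept if conclusions are meant to go beyond the tested messages, and say which is intended. Keep the planned covariates, F-tests and Holm step. These models suit either exposure design.
3. In VI.D, use the same approach for Condition x Topic on the outcomes rated per message (perceived effectiveness and reactance).

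The cost is revised wording and a standard model, with no new data. Section III.B.1 already reports a data-quality result from the Phase 1 study, so the Study 2 data probably exist. If so, the change governs how they are analysed and reported, and should be described as made after collection.

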Sample Size Justification: For Aim 1, Phase 1, Study 2—ONLINE RATING SURVEY: An analytic sample size of 200 participants per group will allow us to detect differences between two groups in terms of perceived message effectiveness. Assuming a pooled standard deviation of 1.0 units, the study would require a minimum sample size of  $n = 199$  for each group to achieve power of 80% and two-sided significance level of  $p = .05$  for detecting a 0.25 unit difference in perceived message effectiveness scores, which has been reported previously in the literature. Under these same parameters, we will be able to detect a 0.25 unit difference in PME scores with 75% probability assuming a significance level of  $p = 0.1$ . As multi-group comparisons are exploratory, we believe this a prior sample size calculation is appropriate. As our desired analytic sample size is  $N = 500$  participants ( $n = 250$  participants per experimental group; AR vs RR messages); we have inflated our overall sample size is inflated by 10% to account for estimated inconsistencies between prescreening and survey responses, resulting in an overall sample size of  $N = 550$ .

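### Study 2's fallback rank tests are described as tests of medians, which they are not; a rejection reported as a median difference can be wrong.

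*Combined protocol and SAP*

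**What the plan says.** Section VI.B (Study 2, online rating survey) first promises mean and median values of the ratings for perceived effectiveness, likeability and reactance. It then turns to group comparisons, labelled exploratory: "In exploratory analyses, we will assess whether there are systematic differences in participants' ratings by message type (AR vs RR"), and likewise by gender, LGBT status, race/ethnicity, age and tobacco user type. The default is on means: "We will test mean differences between groups using t-tests or ANOVA". The switch follows: "If there are violations of assumptions (e.g., normality"), then "we will test median differences between groups using Wilcoxon rank-sum test (two groups) or Kruskal Wallis test (more than 2 groups").

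No diagnostic or threshold for the switch is given, and no condition that the groups' distributions have the same shape.

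The sample size paragraph of the same section is built on a difference in scores: "Assuming a pooled standard deviation of 1.0 units", "for detecting a 0.25 unit difference in perceived message effectiveness scores". The planned analytic size is 250 per group for absolute risk (AR) versus relative risk (RR) messages.

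**The concern.** A rank-sum or Kruskal-Wallis test asks whether values in one group tend to exceed those in another. It becomes a test of medians only under an added assumption, namely that the distributions differ by a shift and otherwise have the same shape. Ratings on a bounded scale need not satisfy that: one group may use both ends of the scale more than another while the medians coincide. The test can then reject, and a report that follows section VI.B would announce a median difference where there is none.

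The same branch changes the quantity compared, from the mean difference used for sizing to a rank-based one, on a trigger that the plan leaves undefined. The comparisons cover six grouping factors and three ratings, so the mislabelling could recur. What is at stake is the correctness of exploratory statements about how groups differ in their ratings.

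**Working it through.** **The plan's own figure.** Section VI.B states a minimum of 199 per group for a 0.25-unit difference with SD 1.0, "to achieve power of 80% and two-sided significance level of" 0.05. With n = 2(z_{1-α/2} + z_{1-β})² SD²/δ²:

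- two-sided 0.05: 2 × (1.960 + 0.842)² / 0.0625 ≈ 251.2, so 252 per group (253 by the exact t calculation);
- two-sided 0.10: 2 × (1.645 + 0.842)² / 0.0625 ≈ 197.8, so 198 (199 by the exact t).

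The 199 therefore does not reproduce at 0.05. That is a separate matter and nothing below rests on it. At the planned 250 per group, power for 0.25 units is 80% at two-sided 0.05. What matters here is that the design quantity is a difference in mean scores.

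**Does a rank-sum rejection imply different medians?** The documents give neither the response scale nor the shape of the scores, so the following is an assumed 5-point example (probabilities for scores 1 to 5):

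- Group A: .03, .09, .23, .45, .20. Mean 3.70, SD 0.98. Cumulative .35 at score 3 and .80 at score 4, so the median is 4.
- Group B: .107, .08, .12, .393, .30. Mean 3.70, SD 1.27. Cumulative .307 at 3 and .70 at 4, so the median is 4.

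Probability that a rating from B exceeds one from A: .08×.03 + .12×.12 + .393×.35 + .30×.80 = .394. Probability of a tie: .03×.107 + .09×.08 + .23×.12 + .45×.393 + .20×.30 = .275. Counting ties as half: .394 + .275/2 = 0.53. The rank test looks for a departure of this quantity from 0.50, so it has something to find although the medians and means agree.

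Rejection rates at two-sided 0.05 (4,000 simulated data sets; a repeat with 10,000 agreed to within about one percentage point):

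| n per group | Rank-sum | Welch t |
|---|---|---|
| 100 | 13.0% | 5.3% |
| 200 | 21.2% | 4.9% |
| 250 | 26.2% | 4.3% |

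A second assumed pair (.16, .04, .50, .24, .06 against its mirror image; both medians 3, both means 3.0) gives 37% for rank-sum and 5.3% for the t-test at 250 per group.

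**Does non-normality alone call for the switch in AR vs RR?** Both groups were given the same skewed distribution, so the correct rate is 5%. With (.55, .22, .12, .07, .04), pooled and Welch t reject in 4.7% at 250 per group. With three other 5-point shapes (skewness -1.25, 1.94 and 3.17) the pooled t rejects in 4.7% to 4.9% at 250 per group. The mean comparison holds its level.

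**Small cells.** The Sample section (III.B.1) expects 57%, 19%, 15% and 6% in the named race/ethnicity groups, leaving 100 - 57 - 19 - 15 - 6 = 3%. Of 500, the largest group is 0.57 × 500 = 285 and the two smallest are 0.06 × 500 = 30 and 0.03 × 500 = 15. With identical skewed distributions in both groups:

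| Shape | Cells | Welch t | Rank-sum |
|---|---|---|---|
| .55, .22, .12, .07, .04 | 30 vs 285 | 6.0% | 4.8% |
| same | 15 vs 285 | 7.6% | 5.0% |
| .75, .13, .06, .04, .02 | 30 vs 285 | 8.1% | 5.0% |
| same | 15 vs 285 | 12.2% | 4.3% |

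At skewness 3.17, Welch reaches 19% at 15 vs 285. The pooled t kept to 5% or below in these runs, but it is exposed to unequal variance: with normal scores, 30 vs 285 and SD 1.5 vs 1.0, it rejects in 16%, rank-sum in 10% and Welch in 5.3%. No single test is best in every listed comparison.

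**The case against.** The strongest reply is that the harm is limited, and much of that stands.

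- The comparisons are declared exploratory.
- The rejection in the example is not spurious: the probability of a higher rating is 0.53, so a real distributional difference is being detected and only the word median is wrong.
- The plan describes medians alongside means. If they are tabulated by group, a false median claim would contradict the table. In the example at 250 per group, the two sample medians were equal in all of 4,000 simulated data sets.
- The exploratory regressions on message type carry no rank-test switch, so an adjusted mean comparison of AR and RR is planned anyway.
- The size of the error rests on constructed distributions and on one score per person in two independent groups, whereas each participant rates several messages.

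These points bound the consequence. They do not make the stated target of the tests correct, and the plan does not say that medians will be tabulated for each comparison.

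Three stronger readings are tempting, and the documents do not support them. First, a reader might extend the point to Phase 2, where "Baseline and post-viewing scores may be transformed if violations of assumptions are detected" (section VI.D). That clause makes no claim about medians and does not name normality; regression assumptions also include linearity and constant variance, which sample size does not cure. Second, a reader might infer that these tests decide which messages advance. No section states such a rule; the protocol describes message refinement through focus groups, interviews and expert review. Third, a reader might conclude that rank tests are unnecessary throughout and that Welch should replace them. That fails for cells of about 15 to 30 people.

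**Conclusion.** The Study 2 wording is wrong as it stands. Rank-sum and Kruskal-Wallis do not test median differences without a shared-shape condition, which the plan does not require. Under an assumed 5-point scale with equal medians and means, rank-sum rejects about 25% of the time at 250 per group. The percentage depends on the assumed shapes; the logical point does not. Kruskal-Wallis was not simulated, but the same reasoning applies.

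For AR versus RR at about 250 per group, non-normality alone gives no reason to leave the mean comparison. The consequence is a mislabelled exploratory finding and a data-driven choice of test, not an invalid primary result. The point is minor in weight and nearly free to correct.

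**What to change.** In section VI.B:

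1. State that the AR versus RR comparison of means is the main result regardless of non-normality. It holds its level at this size and matches the 0.25-unit difference used for sizing.
2. Present rank-sum and Kruskal-Wallis results as a sensitivity analysis, described as differences in distribution, with the probability of a higher rating for two-group comparisons. Remove the reference to medians as the quantity tested.
3. For small race/ethnicity cells (about 15 to 30 people), rank tests may be kept under the same corrected description.

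The cost is a small change in analysis wording and reporting, with no effect on enrolment or data collection. Section III.B.1 already cites a result from Phase 1, so for Study 2 the change may fall mainly on how results are reported.

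### In Study 2, Holm's adjustment after a significant F-test is valid but needlessly conservative for three efficacy types, at a modest cost in power

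*Combined protocol and SAP*

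**What the plan says.** Section VI.B (Aim 1, Phase 1, Study 2 data analysis) introduces the models as exploratory: "We will also run exploratory regression models to evaluate the effect of risk message type". They also cover "efficacy message type (e.g., quit; switch; combination", and the outcomes are listed as "on perceived message effectiveness, likeability, and reactance; controlling for pro- and anti-tobacco marketing exposure". For the efficacy factor, "we will conduct overall F-tests to determine if there is an effect of efficacy message type in each model". The next sentence adds the second layer: "If so, pairwise t-tests will be conducted, and Holm's procedure will be used to control Type I error rate". No reason is given for using both, and no adjustment across the three outcomes is stated.

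The sample size paragraph of the same section concerns a two-group comparison and calls multi-group comparisons exploratory. It gives no number of ratings per efficacy type. Section III.B says each participant sees 3 of 12 efficacy statements, without saying how the 12 divide among the types. Sections III.B and VI.B name only quit, switch and the combination. Section VI.D uses the same F-then-Holm rule for the Phase 2 experiment.

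**The concern.** Both layers guard against the same event. Holm's strictest threshold, 0.05/3 = 0.0167, protects against all three pairwise nulls being true together. With three means that is the global null, which the F-test must already have rejected before any pairwise test is made. A second penalty for the same risk makes a real difference between two wordings easier to miss, with no stronger guarantee in return. Section VI.B offers no other inferential comparison of the three efficacy types, so this is where any loss of sensitivity falls.

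**Working it through.** **The plan's own figure.** The only stated figure is 199 per group for two groups: "Assuming a pooled standard deviation of 1.0 units", 80% power, "for detecting a 0.25 unit difference in perceived message effectiveness scores". By the normal formula, n = 2(z₁₋α/₂ + z₀.₈₀)²(SD/δ)² = 2(1.960 + 0.842)²/0.25² ≈ 252 per group at two-sided 0.05, and 2(1.645 + 0.842)²/0.25² ≈ 198 at two-sided 0.10 (199 on the t distribution). So 199 does not reproduce at the stated level. That is a separate matter and has no bearing on the Holm step, for which the plan states no figure.

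**Logic.** Call the three means Q, S and C. If any two of Q = S, Q = C and S = C hold, so does the third. The cases are:
1. All three equal. A false rejection requires a significant F-test, which has probability 5%.
2. Exactly one pair equal. Only one true null exists, and its single t-test at 0.05 errs at most 5% of the time.
3. No pair equal. No false rejection is possible.

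So the F gate plus unadjusted t-tests gives strong 5% control within each model. Every Holm rejection has p ≤ 0.05, so after the same gate the unadjusted tests reject everything that Holm rejects, and sometimes more.

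**Inputs for the size.** SD 1.0 and a 0.25 shift come from the sample size paragraph of section VI.B. Ratings per type are an assumption, shown as a range. A value of 167 is 500/3, as if each participant contributed one rating. A value of 500 follows from 500 × 3 = 1,500 ratings, divided by 3 types, if the 12 statements split evenly.

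**Simulation.** 200,000 trials per setting, three independent normal groups, pooled variance, one type shifted by 0.25:

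| Ratings per type | Power per true difference, F + unadjusted | F + Holm | Loss (points) |
|---|---|---|---|
| 167 | 55% | 48% | 7 |
| 200 | 64% | 57% | 7 |
| 250 | 75.5% | 68.6% | 7 |
| 500 | 97.3% | 95.5% | 2 |

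- Power to find both true differences is 55.4% vs 43.7% at 200 per type, and 95.7% vs 92.4% at 500.
- At 500 per type with a smaller shift of 0.15 SD, the loss per contrast is again about 7 to 8 points.
- Family-wise error, unadjusted vs Holm after the gate, is 0.050 vs 0.042 under the global null and 0.050 vs 0.050 with the third type far away. With a 0.25 shift and 200 per type it is 0.048 vs 0.029.
- For contrast, unadjusted t-tests without any gate give 0.122 under the global null.

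**Where the argument stops.** With more groups the F gate alone fails. Worst-case family-wise error is 0.12 for 4 groups, 0.37 for 7 and 0.44 for 8.

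**The case against.** The strongest reply is that nothing planned is wrong. F then Holm is a valid, mildly conservative choice in models labelled exploratory, and no power claim rests on it. That stands, and it makes this an efficiency point.

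A second reply is that 167 per type does not fit three statements per participant. That also stands. About 500 per type is more plausible, and the loss at a 0.25 shift is then about 2 points. Within-person correlation does not restore the larger loss. Drawing 3 of 12 statements with a random participant effect gave a contrast SD of 0.062 at correlation 0.3 and 0.060 at 0.5, against 0.063 for 500 independent ratings per type.

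A third reply is that Holm needs only valid pairwise p-values, while the alternative also needs a calibrated F-test. This is weak, because a model that ignores repeated ratings would miscalibrate the t-tests as well.

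A reader might infer that the extra adjustment could distort the Phase 2 efficacy arm. The documents do not support that. Table 2 carries quit, switch and combined wording into Phase 2 whatever this test shows, and no passage selects an efficacy type on these comparisons. A reader might also infer that Holm buys nothing at all. It adds nothing to the 5% guarantee, but realised error does fall in some settings.

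**Conclusion.** The point holds as a minor, optional improvement. For exactly three efficacy types within one model, Holm after a significant F-test is redundant for 5% family-wise control. For one type shifted by 0.25 SD, it costs about 7 points of power per contrast at 167 to 250 independent ratings per type and about 2 points at about 500.

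This rests on there being three types (the list is introduced as an example, though no other type is named), on valid F- and t-tests from one model, and on an assumed number of ratings per type. The guarantee applies to each outcome separately. Neither procedure controls error across perceived effectiveness, likeability and reactance together.

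**What to change.** In section VI.B, for the three-level efficacy factor only, replace the Holm sentence with a statement of this kind: if the overall F-test is significant at 0.05, each of the three pairwise t-tests from the same fitted model is made at 0.05, which holds family-wise error at 5% for each outcome by closed testing. Add that the model accounts for repeated ratings by the same participant, for example with a random participant effect.

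Keep Holm if more than three efficacy types are compared, and leave it in place in section VI.D, where there are more than three conditions.

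The Phase 2 sample description in section III.B.1 already cites a result from the Phase 1 study, so Study 2 data may have been seen. If so, report this analysis beside the planned Holm analysis and label it post hoc. The cost is a sentence or two of wording. No extra data are needed and the 5% guarantee is kept, though realised error would be somewhat higher than under Holm in some settings.
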